### Exclusion criteria:

- Patients younger than 18 years of age.
- Patients with the diagnosis of inflammatory bowel disease.

## **Patients selection and follow-up:**

The first 100 patients fulfilling the inclusion criteria will be included in the prospective phase of the study. Patients will be identified by means of daily report of the positive results from the Microbiology lab. They will be prospectively followed 8 weeks after the end of treatment for the episode of CDI. If there are one or more recurrences, the follow-up will endure until 8 weeks after the end of the last CDI treatment.

They will be retrospectively compared with patients diagnosed with a first episode of CDI during the previous year (2015) in which there was not a systematical intervention by a member of the Infectious Diseases Unit.

To ensure comparability, patients from the retrospective period will be chosen and matched with patients included in the prospective period according to the severity of the initial episode of CDI and to the Charlson Age-Comorbidity Index (CACI).

If patients diagnosed during 2015 are not enough to fulfil those comparison criteria, we will search backwards through patients diagnosed with a first episode of CDI during 2014 to be matched.

The retrospective follow-up will also endure until 8 weeks after the end of the last CDI treatment.

## **Microbiological methods:**

All unformed stools (taking the shape of the container) from patients with a clinical suspicion of CDI will be processed immediately or, when logistically unfeasible, kept at 4° C or frozen at -70° C until processing. Samples will be simultaneously tested for GDH

and toxin A/B with a single immunochromatographic assay, the TechLab® C. diff Quik Chek Complete™ (Inverness Medical Innovations, Princeton, NJ, USA). For samples with discordant results (GDH-positive, toxin A/B-negative), toxin production will be confirmed by the Xpert® C. difficile PCR assay (Cepheid, Sunnyvale, CA, USA).

The diagnostic algorithm used during the retrospective period was exactly the same, as it was implemented in our hospital in February 2011.

### **Specific "bundle" of measures for patients with ICD:**

These measures are based in well-known and evidence-based elements that reduce the incidence and limit the spreading of *Clostridium difficile* (see references 6,13,22-25):

Systematic evaluation of all patients diagnosed with CDI by an Infectious Disease expert with the implementation of the following interventions:

- To ensure compliance with clinical practice guidelines about specific treatment for CDI, depending on the severity of the episode and the existence of previous episodes, thus improving the prognosis of these patients and avoiding side effects.
- To optimize concomitant antibiotic therapy ("antimicrobial stewardship") through the following interventions:
  - To remove unnecessary treatments.
  - To shorten antibiotic courses as far as possible.
  - To avoid, if possible, broad-spectrum or high risk for developing CDI antibiotics.
- To reduce indiscriminate use of proton-pump inhibitors (PPI) or H2 receptor antagonists (H2 blockers).
- To provide clear instructions to patients and their families about the measures that should be implemented at home after discharge. To answer their questions and calm their fears about the CDI and need for isolation.
- To ensure appropriate monitoring during the period of greatest risk of relapse (8 weeks after completion of antibiotic treatment for CDI) in order to reduce as far as possible, the number of relapses by the following interventions:
  - Personalized assistance by telephone or by email for early consultation in case of recurrence of symptoms, in order to make:
    - Early diagnostic of relapses.
    - Appropriate treatment of subsequent episodes.

- Detection of patients who could benefit from fecal microbiota transplantation.
- o Personalized assistance by telephone or by email for consultation in case of necessity of a new antibiotic course in order to:
  - Avoid unnecessary antimicrobial treatments.
  - Choose the antibiotic class with less risk of selecting *C. difficile*.
  - Evaluate preventive measures in an attempt to prevent the development of CDI.

## **Definitions:**

**Diarrhoea:** Loose stools, i.e. taking the shape of the receptacle or corresponding to Bristol stool chart types 5–7, plus a stool frequency of three stools in 24 or fewer consecutive hours or more frequently than is normal for the individual.

An **episode of CDI** is defined as: A clinical picture compatible with CDI and microbiological evidence of free toxins and the presence of *C. difficile* in stool without reasonable evidence of another cause of diarrhoea or Pseudomembranous colitis as diagnosed during endoscopy, after colectomy or on autopsy.

**Mild or moderate CDI/non-severe CDI:** Diarrhoea without systemic symptoms, leukocytosis with a white blood cell count lower than 15,000 cells/mL and a serum creatinine level less than 1.5 times the premorbid level.

**Severe CDI:** systemic symptoms of infection and/or leukocytosis with a white blood cell count of 15,000 cells/mL or higher or a serum creatinine level greater than or equal to 1.5 times the premorbid level.

**Severe Complicated CDI/Fulminant CDI:** was defined by the presence of severe disease accompanied by life-threatening conditions such as ileus, toxic megacolon, refractory hypotension and/or multi-organ failure attributable to CDI.

**Ileus:** Signs of severely disturbed bowel function such as vomiting and absence of stool with radiological signs of bowel distension.

**Toxic megacolon:** Radiological signs of distension of the colon (>6 cm in transverse width of colon) and signs of a severe systemic inflammatory response (nausea, vomiting, dehydration, lethargy or tachycardia addition to fever and abdominal pain).

**Leukocyte count to consider severity of the CDI:** Any white blood cell count (WBC) measured between two days before and two days following the date of the stool sample. If a patient had WBC measured on the date of the stool sample then this was selected. If they did not have WBC measured on the date of the stool sample but had WBC measured between one day before and one day following their stool sample, then this was selected. If they did not have WBC measured between one day before and one day following their stool sample but had WBC measured between two days before and two days following their stool sample, then this was selected. If they did not have WBC measured on the date of the stool sample but had WBC measured both one day before and one day following the date of stool sample, or had WBC measured both two days before and two days after the stool sample but not between these measurements, then the highest of the two measurements was selected.

**Definition of treatment response:** Treatment response is present when either stool frequency decreases or stool consistency improves and parameters of disease severity (clinical, laboratory, radiological) improve and no new signs of severe disease develop.

**Definition of recurrent CDI:** Recurrence is present when CDI re-occurs within 8 weeks of successfully completing treatment for CDI.

**Duration of diarrhea:** was the sum of days from day 1 to the last day with diarrhea, followed by 2 or more days without diarrhea.

**Antibiotics of high, medium and low risk for CDI:** according to the table proposed by Aldeyab et al (S3. J Antimicrob Chemother 2012; 67: 2988–2996).

**Table S3.** Risk classification of antibiotics

High risk	Medium risk	Low risk
Second-generation cephalosporins [J01DC; cefaclor, cefuroxime].	Combinations of penicillins including $\beta$ -lactamase inhibitors [J01CR; amoxicillin/clavulanic acid]	Combinations of penicillins including $\beta$ -lactamase inhibitors [J01CR; piperacillin/tazobactam] Penicillins with extended spectrum [J01CA; amoxicillin, ampicillin; pivmecillinam] $\beta$ -Lactamase-sensitive penicillins [J01CE; phenoxymethylpenicillin, benzylpenicillin]
Third-generation cephalosporins [J01DD; cefotaxime, ceftazidime, ceftriaxone]	Macrolides [J01FA; azithromycin, clarithromycin, erythromycin]	$\beta$ -Lactamase-resistant penicillins [J01CF; flucloxacillin] First-generation cephalosporins [J01DB; cefalexin, cefradine] Trimethoprim and derivatives [J01EA] Carbapenems [J01DH; ertapenem, meropenem] Combination of sulphonamides and trimethoprim [J01EE] Aminoglycosides [J01GB; amikacin, gentamicin, neomycin]
Fluoroquinolones [J01MA; mainly profloracin; others: norfloxacin; ofloxacin; levofloxacin]		Glycopeptides [J01XA; teicoplanin, vancomycin] Steroid antibacterials [J01XC; sodium fusidate] Imidazole derivatives [J01XD; metronidazole] Nitrofurant derivatives [J01XE; nitrofurantoin] Other antibacterials [J01XX; linezolid]
Lincosamides [J01FF; clindamycin]		Tetracyclines [J01A; demeclocycline, doxycycline, minocycline, oxytetracycline, tetracycline, lymecycline, tigecycline]

**Charlson Age-Comorbidity Index (CACI):** This index will be calculated by the electronic calculator [www.pmidcalc.org/7722560](http://www.pmidcalc.org/7722560) (Charlson M, Szatrowski TP, Peterson J, Gold J. Validation of a combined comorbidity index. J Clin Epidemiol. 1994;47(11):1245-51).

Based on previous authors (26-29) we proposed several terms to describe the appropriateness of prescription in each episode:

- **Right choice:** According to the current guidelines, the medication is effective for the condition and also used at optimal doses and duration, without duplication or association with unnecessary drugs.
- **Inappropriate/suboptimal prescription:**
  - o **Overuse:** inclusion of unnecessary medication for the condition, which may result in an increased risk of adverse reactions, drug-drug interactions and increased costs.
  - o **Underuse:** omission of a drug when there is a clear indication and no contraindications. The failure to prescribe essential medications may result in the worsening of the illness or therapeutic failure.

Our definition of right choice will be judged according to the latest European Society of Clinical Microbiology and Infectious Diseases guidelines (Debast SB, Bauer MP, Kuijper EJ; Committee. European Society of Clinical Microbiology and Infectious Diseases:

update of the treatment guidance document for *Clostridium difficile* infection. Clin Microbiol Infect. 2014 Mar;20 Suppl 2:1-26).

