## Hypothesis

1. A bundle of measures specifically designed for patients with ICD and applied by and Infectious Diseases expert would improve the prognosis and reduce the risk of recurrence.
2. Some measures have proved to be effective to improve the prognosis of patients with a first episode of CDI. Probably the most relevant action is to stop the antibiotic treatment as soon as possible (grade of recommendation All according

to the IDSA guidelines), or at least to choose a low-risk antimicrobial treatment with minimum detrimental effect over the patient's microbiota. This measures cannot always be applied, but we hypothesize that an early assessment and monitoring by an Infectious Diseases expert would encourage attending physicians to evaluate the necessity of the inciting antimicrobial treatment and enable the decision of discontinue it, without substantial risk for the patient.

3. Although treatments shorter than 10 days of metronidazole have proved to increase the risk of recurrence and the recommendation is 10-14 days of metronidazole for a first mild or moderate episode of CDI (grade of recommendation AI), courses of 7 days are frequently prescribed. An initial assessment by an Infectious Diseases expert who makes a non-impositive recommendation would increase physicians' compliance with evidence-based recommendations.
4. Although oral vancomycin is the drug of choice for an initial episode of severe CDI (grade of recommendation BI) and vancomycin administered orally (and per rectum, if ileus is present) with or without intravenously administered metronidazole is the regimen of choice for the treatment of severe, complicated CDI, however, it is relatively frequent that the severity of the episode is not accurately assessed at diagnosis, which delays the start of appropriate therapy. An initial assessment by an Infectious Diseases expert who makes a non-impositive recommendation would increase physicians' compliance with evidence-based recommendations.
5. Although metronidazole should not be used beyond the first recurrence of CDI or for long-term chronic therapy because of potential for cumulative neurotoxicity, it is not uncommon that patients with multiple recurrences receive several courses of metronidazole. Patients with multiple recurrences would benefit from a close follow-up by an Infectious Diseases expert who appropriately diagnoses and treats every episode, following the evidence-based recommendations.

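### The white-cell threshold in both severity definitions is given per mL, so as written no patient with a plausible measured count can be classed as mild/moderate for matching

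*Combined protocol and SAP*

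**What the plan says.** All references are to the combined protocol and SAP.

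- **Definitions, severe CDI.** Any one of three findings is enough. The white-cell finding is "leukocytosis with a white blood cell count of 15,000 cells/mL or higher". The other two are systemic symptoms and a creatinine that has reached 1.5 times its earlier value.
- **Definitions, mild or moderate (non-severe) CDI.** The patient has diarrhoea, no systemic symptoms, "leukocytosis with a white blood cell count lower than 15,000 cells/mL", and a creatinine below 1.5 times the earlier value.
- **Definitions, severe complicated/fulminant CDI.** This third level "was defined by the presence of severe disease accompanied by life-threatening conditions such as ileus, toxic megacolon, refractory hypotension", or by organ failure due to CDI. It is not set by the white-cell count alone.
- **Definitions, leukocyte count.** A detailed rule selects which count is used to judge severity, from those "measured between two days before and two days following the date of the stool sample". It gives no unit.
- **Patients selection and follow-up.** Historical controls are to be "matched with patients included in the prospective period according to the severity of the initial episode of CDI" and on the Charlson Age-Comorbidity Index (CACI).
- **Data collection and analysis.** Comparable historical patients are chosen by the severity of the first episode; CACI is not mentioned here.
- **Hypothesis, item 3.** The authors discuss "10-14 days of metronidazole for a first mild or moderate episode of CDI", so they expect such episodes.

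**The concern.** The unit turns the threshold into a count far below anything that could be called leukocytosis, yet the line uses that word. If the number is applied as written, it puts every measured count on the same side of the cut.

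This is an operative rule. It decides which historical patient is an acceptable match for which prospective patient. The study is a non-randomised before-after comparison, and matching is the stated means of making the two groups comparable. The recurrence comparison is then to be made by conditional logistic regression (Statistical Plans), which takes the matched sets as given. If severity were coded by a rule that cannot tell mild from severe, the pairs could differ in true severity while appearing matched. Adjusting for a severity covariate coded by the same rule would not repair that.

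A second, smaller defect is in the wording. The non-severe line appears to require leukocytosis, which a patient with a normal count does not have.

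**Working it through.** The threshold is a definition, not a computed figure, so there is no plan calculation to reproduce. The check is a unit conversion followed by a reading of the two class definitions.

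**Step 1. Convert the unit.** 1 mL = 1,000 microlitres, so

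15,000 cells/mL / 1,000 = 15 cells/microlitre = 0.015 x 10^9/L.

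**Step 2. Compare with possible patient counts.** The documents give no typical white-cell count or normal range, so a deliberately wide range is assumed. Ratio = (count per microlitre x 1,000) / 15,000.

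| Assumed count (per microlitre) | Same count per mL | Ratio to threshold | At or above 15,000/mL? |
|---|---|---|---|
| 100 | 100,000 | 6.7 | yes |
| 4,000 | 4,000,000 | 267 | yes |
| 11,000 | 11,000,000 | 733 | yes |
| 30,000 | 30,000,000 | 2,000 | yes |

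No count in the range falls below the threshold.

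**Step 3. Apply the definitions to a patient with no systemic symptoms and no creatinine rise.** The result depends on how much weight the word leukocytosis carries.

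| Reading | Raised count | Normal count |
|---|---|---|
| The number alone decides | severe | severe |
| Leukocytosis is a separate condition that must also hold | severe, whatever the size of the rise | not severe, but not non-severe either, because the count is not below 15,000/mL |

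The non-severe class is empty on both readings. On the second, the number does no work and patients with a normal count belong to neither class. A patient with no count in the two-day window has no value to classify on this criterion.

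**Step 4. Ask whether the unit alone explains the problem.** Suppose the unit were corrected. The non-severe line would still join leukocytosis to a count below the threshold, so a patient with a normal count would still not fit it cleanly. The wording needs its own repair.

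**Step 5. Trace what is affected.**

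- Affected: the split between non-severe and severe, as used for matching.
- Not affected: the split between severe and fulminant disease, which rests on ileus, megacolon, hypotension or organ failure; and CACI, the other matching variable.

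**The case against.** The strongest answer is that any clinician would see the slip. The word leukocytosis sits beside the number and signals that a raised count is meant. For harm to follow, someone would have to convert laboratory counts to a per-mL scale and then accept a normal count as leukocytosis. The documents describe no such coding rule, only collection from medical records into a coded database. This stands: the issue is a risk from literal application, not a demonstrated failure.

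The unit may also be an artefact of reading the PDF, with a micro sign turned into an m. This cannot be excluded without the source page. Against it, the Greek letters beta (antibiotic risk table) and chi (Statistical Plans) came through correctly, and the unit is the same in both definitions.

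Three stronger conclusions are tempting, and the documents support none of them:

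- *Every patient is severe.* This holds only if the number alone decides. If leukocytosis must also be present, a patient with a normal count is left unclassified. What holds on both readings is that no patient with a measured count in the assumed range can be non-severe.
- *Matching fails altogether, on its main variable.* Patients selection and follow-up names severity and CACI without ranking them. Data collection and analysis names severity alone but does not withdraw CACI. Fulminant disease also remains distinct.
- *The recurrence comparison is biased by a known amount.* The documents give neither the severity imbalance nor the recurrence difference by severity that such a figure would need. The planned model is also to be adjusted for confounders.

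Nor can one say that the scoring of treatment as appropriate is wrong. That judgement is tied to the named European guideline, and no text says that the number in the Definitions section is used for it.

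**Conclusion.** The point stands in limited form. Both severity definitions carry a threshold that equals 15 cells per microlitre, nothing elsewhere in the document corrects it, and it conflicts with the word leukocytosis in the same lines. Applied as written, it leaves the mild/moderate class empty for any measured count between 100 and 30,000 per microlitre, a range assumed here. The written rule therefore cannot separate non-severe from severe patients for matching. The effect on the recurrence estimate cannot be sized from the documents.

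The likely explanation is a mislabelled unit that the study team would read past. A correction is still warranted, because this is a decision threshold with its own count-selection rule and it determines the choice of historical controls. Confidence is moderate, because the source page has not been seen.

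**What to change.** 1. Check the unit in both definitions against the source page.
2. If it does read per mL, reconcile number and unit in both lines with the laboratory's reporting unit and with the European guideline that the Definitions section names. Which cut-off is right is for the sponsor to settle from those sources; this review does not propose one.
3. Reword the non-severe line so that it asks for a count below the threshold and does not require leukocytosis. A patient with a normal count and no other criterion then falls in exactly one class.
4. State the unit in the count-selection rule, and apply the same coded severity rule to both periods before matching.

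The cost is two lines of definition text and one coding check. No new data are needed.

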### Secondary objectives:

- To reduce the rate of second and further recurrences by increasing the compliance with clinical practice guidelines (appropriate length and choice of drug for the treatment of first and further recurrences).
- To discontinue or to reduce the spectrum of unnecessary antibiotic treatments in this population ("antimicrobial stewardship"), especially during the episode of CDI and during the following 8 weeks.
- To discontinue inappropriate treatment of asymptomatic patients colonized by *Clostridium difficile*.
- To identify clinical and biological markers that could be used as predictors of recurrence.
- To identify patients with a high number of recurrences, that could benefit from novel or experimental treatments.

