### **Data collection and analysis**

Patients in the pre-intervention period will be retrospectively identified from microbiological data. All isolates of *Clostridium difficile* from 2015 (and 2014, if necessary) will be revised backwards to choose comparable patients with those included in the prospective period, according to the severity of the first episode.

Data will be collected from electronic medical records which include daily medical evaluations and daily treatments administered to the patient.

Patients in the intervention period will be identified by daily reporting of positive tests for CDI from the Microbiology laboratory and prospectively followed by a member of the research team.

The variables will be collected in a coded database for further analysis.

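### The protocol does not say who grades prescribing appropriateness, when, or whether masked to period, so a compliance or stewardship gain created by the grading cannot be excluded

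*Combined protocol and SAP*

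**What the plan says.** **What is advised.** Under the bundle heading, the intervention is "Systematic evaluation of all patients diagnosed with CDI by an Infectious Disease expert". Its first component is "To ensure compliance with clinical practice guidelines about specific treatment for CDI, depending on the severity of the episode"; the next covers removing, shortening or narrowing other antibiotics. For the comparison patients, Patients selection and follow-up says that "there was not a systematical intervention by a member of the Infectious Diseases Unit".

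**What is graded.** The Definitions section classes each prescription as right choice, overuse or underuse. Right choice requires that "the medication is effective for the condition and also used at optimal doses and duration, without duplication or association with unnecessary drugs". Overuse is "inclusion of unnecessary medication for the condition, which may result in an increased risk of adverse reactions, drug-drug interactions and increased costs". The reference standard is given in one sentence: "Our definition of right choice will be judged according to the latest European Society of Clinical Microbiology and Infectious Diseases guidelines". The guideline cited there is a 2014 treatment guidance document for CDI.

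**Where the grades matter.** The primary objective is fewer recurrences, with better guideline compliance named as one of the means. One secondary objective is "To discontinue or to reduce the spectrum of unnecessary antibiotic treatments in this population", with emphasis on the CDI episode and the 8 weeks after it.

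**How data are captured.** Under Data collection and analysis, intervention patients are "prospectively followed by a member of the research team", while comparison patients are found retrospectively from microbiology results. Electronic records that include daily treatments are the data source.

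No section names the assessor, masks the assessor to period, separates adviser from assessor, or plans a second reading or an agreement check.

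**The concern.** The items graded as outcomes are the same items that the intervention gives advice on. If an assessor knows the period, borderline 2017 prescriptions that followed the advice may be graded more kindly than similar prescriptions from 2015. The information can differ too: a reason for an antibiotic that the 2017 team knew at first hand may never have been written in a 2015 chart, so that the earlier course looks unnecessary.

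Compliance and stewardship are how the protocol expects the bundle to work. A difference that came from grading would be reported as a change in prescribing, and would be offered as the explanation for any change in recurrence. If recurrence did not change, it could become the main positive result.

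**Working it through.** The plan states no expected compliance rate, and no sample size or power for compliance, so there is no figure of its own to reproduce. The check has two parts.

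**1. How far each graded component is tied down**

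| Component | Standard in the protocol | Room for judgement |
|---|---|---|
| CDI drug, dose, duration | One named 2014 guideline; treatments are in the records | Small once severity is fixed |
| Severity class, on which guideline treatment depends | Numerical white-cell and creatinine thresholds, and a rule for choosing the white-cell count within two days either side of the sample | Limited to the systemic-symptoms item, which has no threshold |
| Overuse | Defined by the word 'unnecessary' | Large; the definition is circular |
| Underuse | Omission despite a clear indication | Moderate |
| Need for a concomitant antibiotic | None stated; the named guideline concerns treatment of CDI, and the antibiotic risk table ranks drugs by CDI risk, not by need | Largest |

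The standard for CDI treatment is therefore the same for 2015 and 2017. If controls have to be drawn from 2014, as the protocol allows, some could predate the guideline's March 2014 publication.

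**2. What a grading shift would do**

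Inputs:
- From the protocol: 100 intervention patients (Patients selection and follow-up), equal groups and a two-sided 5% level (Statistical Plans).
- Assumed: true compliance a = 0.5, 0.6 or 0.7 in both periods; grading raises the 2017 figure to b = a + d, with d = 0.05, 0.10 or 0.15; an unpaired test.

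Formulas: SE = √[a(1−a)/100 + b(1−b)/100]; probability of p < 0.05 = Φ(d/SE − 1.96) + Φ(−d/SE − 1.96).

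Example with a = 0.5 and d = 0.10: SE = √(0.0025 + 0.0024) = 0.0700; d/SE = 1.429; probability = Φ(−0.531) + Φ(−3.389) = 0.298.

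| Shift d | a = 0.5 | a = 0.6 | a = 0.7 |
|---|---|---|---|
| 0.05 | 10.9% | 11.3% | 12.5% |
| 0.10 | 29.8% | 32.0% | 37.6% |
| 0.15 | 58.3% | 63.1% | 73.3% |

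The nominal figure is 5%.

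A second model puts the errors into individual grades, with true compliance of 40-70% in both periods and a pooled-variance test:
- 10% of compliant 2015 courses marked down: apparent gain 4-7 points, p < 0.05 in 9-18%.
- 5% of compliant 2015 courses marked down and 5% of non-compliant 2017 courses marked up: gain 5 points, p < 0.05 in 11-12%.
- The same with 10% each way: gain 10 points, p < 0.05 in 29-33%.

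The two models agree closely at 5 points and overlap at 10. The protocol plans paired tests; positive correlation within pairs would shrink the SE, so the same shift would reach significance somewhat more often.

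**The case against.** The strongest reply is that the sentence on right choice points to an external, published standard that is the same for 2015 and 2017, applied to recorded drugs and dates. Severity is mostly numerical. The expert's advice is explicitly not binding, so what is graded is the attending physician's decision. The protocol also already contains an ATC-coded high/medium/low-risk antibiotic table that needs no view on necessity. The study calls itself exploratory, and its primary outcome does not use these grades.

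Most of this stands, and it narrows the point. It does not reach concomitant antibiotics, where no standard of need exists, or the circular definition of overuse. The risk table helps only if it is made the basis of the comparison, which the plan does not say.

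A reader might infer more: that the advising team itself does the grading, live in 2017 and with hindsight for 2015, so that the gain is self-scored. The documents do not say so. Only follow-up is described as prospective; grading could be done later from records for both periods, with the later course equally visible. Grading by the research team is a natural reading, because it follows the 2017 patients and alone has access to the study database (Ethical aspects, in a sentence about the pre-intervention group), but it remains an inference.

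**Conclusion.** The point holds as an omission. Assessor, timing and masking are unspecified, and 'unnecessary' has no criterion, so a between-period difference in compliance or stewardship could arise in part from grading. The exposure is greatest for concomitant antibiotics and smaller for CDI drug, dose and duration. It affects the evidence on mechanism and the secondary objectives that depend on these grades. Appropriateness grades do not enter the definition of recurrence.

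The percentages above are conditional on assumed shifts and base rates and on an unpaired test. They show that a shift of 5 points would already roughly double the nominal 5% error rate, and that 10 points would raise it about six- to eightfold. They are not evidence that any such shift will occur. The change is worth making before the control charts are opened, but the primary analysis does not depend on it.

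**What to change.** **CDI treatment.** Before control charts are opened, lock a table that turns the already named guideline into rules on recorded fields: CDI drug, route, dose, start and stop dates, episode number and severity class. Severity should use the protocol's own definitions and its white-cell-count window. Grade the systemic-symptoms item from recorded findings listed in advance. Run the table identically on both periods.

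**Stewardship.** Make the between-period comparison on recorded non-CDI antibiotic use: days of therapy, and use by the protocol's own high/medium/low-risk table. Cover the CDI episode and the following 8 weeks, with the same record sources for both periods. An in-hospital count alone would miss use after discharge, which the objective and the telephone and email advice both cover. Report judged 'unnecessary' use as supportive only.

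**Cost.** Writing the table and a short program; no extra assessor. There are three drawbacks. A rule cannot credit individually justified exceptions. Total use is not the same as unnecessary use. Use after discharge may be less completely recorded for controls, so its completeness should be reported by period.
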